10.1.1.4 Preexisting Medical Conditions (Baseline Conditions)

A preexisting medical condition should be recorded as an AE or SAE only if the frequency, severity, or character of the condition worsens during the study. When recording such events on an Adverse Event CRF, it is important to convey the concept that the preexisting condition has changed by including applicable descriptors (e.g., “more frequent headaches”).

10.1.1.5 Overdose

Refer to **Section 7.3.2** for a definition of pembrolizumab overdose.

- If an adverse event(s) is associated with (“results from”) the overdose of pembrolizumab, the adverse event(s) is reported as a serious adverse event, even if no other seriousness criteria are met.
- If a dose of pembrolizumab meeting the protocol definition of overdose is taken without any associated clinical symptoms or abnormal laboratory results, the overdose is reported as a non-serious Event of Clinical Interest (ECI), using the terminology “accidental or intentional overdose without adverse effect.”

10.1.2 Grading and Relationship to Drug

The descriptions and grading scales found in the CTEP Version 4 of the NCI Common Terminology Criteria for Adverse Events (CTCAE) will be utilized for AE reporting. CTEP Version 4 of the CTCAE is identified and located at:

http://ctep.cancer.gov/protocolDevelopment/electronic_applications/ctc.htm.

AEs not covered by specific terminology listed should be reported with common medical terminology, and documented according to the grading scales provided in the CTCAE Version 4.

The relationship of event to study drug will be documented by the Investigator as follows:

- **Unrelated:** The event is clearly related to other factors such as the participant’s clinical state, other therapeutic interventions or concomitant drugs administered to the participant.

- **Unlikely:** The event is doubtfully related to investigational agent(s). The event was most likely related to other factors such as the participant’s clinical state, other therapeutic interventions, or concomitant drugs.
- **Possible:** The event follows a reasonable temporal sequence from the time of drug administration, but could have been produced by other factors such as the participant’s clinical state, other therapeutic interventions or concomitant drugs.
- **Probable:** The event follows a reasonable temporal sequence from the time of drug administration, and follows a known response pattern to the study drug. The event cannot be reasonably explained by other factors such as the participant’s clinical state, therapeutic interventions or concomitant drugs.
- **Definite:** The event follows a reasonable temporal sequence from the time of drug administration, follows a known response pattern to the study drug, cannot be reasonably explained by other factors such as the participant’s condition, therapeutic interventions or concomitant drugs; AND occurs immediately following study drug administration, improves upon stopping the drug, or reappears on re-exposure.

10.1.3 Reporting Adverse Events

Table 8 Guidelines for Routine Adverse Event Reporting for Phase 1 Studies (Regardless of Expectedness)

Attribution	Grade 1	Grade 2	Grade 3	Grade 4
Unrelated	X	X	X	X
Unlikely	X	X	X	X
Possible	X	X	X	X
Probable	X	X	X	X
Definite	X	X	X	X

Table 9 Guidelines for Routine Adverse Event Reporting for Pilot, Phase 2, and Phase 3 Studies (Regardless of Expectedness)

Attribution	Grade 1	Grade 2	Grade 3	Grade 4
Unrelated			X	X
Unlikely			X	X
Possible	X	X	X	X
Probable	X	X	X	X
Definite	X	X	X	X

Routine AEs occurring between the start date of intervention until 30 days after the last intervention, or until the event has resolved, the study participant is lost to follow-up, the start of a new treatment, or until the study investigator assesses the event(s) as stable or irreversible, will be reported. New information will be reported after it is received.

10.2 Serious Adverse Events

10.2.1 Definition

A serious adverse event (SAE) is any adverse event (experience) that in the opinion of either the investigator or sponsor results in **ANY** of the following:

- Death.
- A life-threatening adverse event (experience). Any AE that places a participant or participants, in the view of the Investigator or sponsor, at immediate risk of death from the reaction as it occurred. It does **NOT** include an AE that, had it occurred in a more severe form, might have caused death.
- Inpatient hospitalization or prolongation of existing hospitalization (for > 24 hours).
- A persistent or significant incapacity or substantial disruption of the ability to conduct normal life functions.
- A congenital anomaly or birth defect.
- Important Medical Event (IME) that, based upon medical judgment, may jeopardize the participant and may require medical or surgical intervention to prevent one of the outcomes listed above.
- Is associated with an overdose
- Is a new cancer (that is not a condition of the study)

10.2.2 Reporting Serious Adverse Events

For the time period beginning when the consent form is signed until treatment allocation/randomization, any serious adverse event, or follow up to a serious adverse event, including death due to any cause that occurs to any participant must be reported within 24 hours to the Sponsor and within 2 working days to Merck Global Safety if it causes the participant to be excluded from the trial, or is the result of a protocol-specified intervention, including but not limited to washout or discontinuation of usual therapy, diet, placebo treatment or a procedure.

For the time period beginning at treatment allocation/randomization through 90 days following cessation of treatment, or 30 days following cessation of treatment if the participant initiates new anticancer therapy, whichever is earlier, any serious adverse event, or follow up to a serious adverse event, including death due to any cause whether or not related to the Merck product, must be reported within 24 hours to the Sponsor and within 2 working days to Merck Global Safety.

SAEs identified as an Unanticipated Problem by the Investigator must be reported. Please refer to **Section 10.7.2** for details on reporting Unanticipated Problems.

Additionally, any serious adverse event, considered by an investigator who is a qualified physician to be related to the investigational drug, that is brought to the attention of the

investigator at any time outside of the time period specified in the previous paragraph, also must be reported immediately to the Sponsor and to Merck.

10.3 Events of Clinical Interest (ECIs)

Refer to the separate guidance document entitled “Event of Clinical Interest Guidance Document” for detailed instruction regarding identification, evaluation and management of ECIs and irAEs.

Participants should be assessed for possible ECIs prior to each dose. Lab results should be evaluated and participants should be asked for signs and symptoms suggestive of an immune-related event. If lab results or symptoms indicate a possible immune-related ECI, then additional testing should be performed to rule out other etiologic causes. If no other cause is found, then it is assumed to be immune-related.

Any Grade 3 or higher event that the investigator considers to be immune-related should be reported as an ECI regardless of whether the specific event term is in **Table 10 and reported to Merck within 24 hours** from the time the Investigator/physician is aware of such an occurrence. Adverse events that are both an SAE and an ECI should be reported one time as an SAE only, however the event must be appropriately identified as an ECI as well in the database.

Table 10 Events of Clinical Interest

Pneumonitis (reported as ECI if \geq Grade 2)		
Acute interstitial pneumonitis	Interstitial lung disease	Pneumonitis
Colitis (reported as ECI if \geq Grade 2 or any grade resulting in dose modification or use of systemic steroids to treat the AE)		
Intestinal Obstruction	Colitis	Colitis microscopic
Enterocolitis	Enterocolitis hemorrhagic	Gastrointestinal perforation
Necrotizing colitis	Diarrhea	
Endocrine (reported as ECI if \geq Grade 3 or \geq Grade 2 and resulting in dose modification or use of systemic steroids to treat the AE)		
Adrenal Insufficiency	Hyperthyroidism	Hypophysitis
Hypopituitarism	Hypothyroidism	Thyroid disorder
Thyroiditis	Hyperglycemia, if \geq Grade 3 and associated with ketosis or metabolic acidosis (DKA)	
Endocrine (reported as ECI)		
Type 1 diabetes mellitus (if new onset)		
Hematologic (reported as ECI if \geq Grade 3 or any grade resulting in dose modification or use of systemic steroids to treat the AE)		
Autoimmune hemolytic anemia	Aplastic anemia	Thrombotic Thrombocytopenic Purpura (TTP)
Idiopathic (or immune) Thrombocytopenia Purpura (ITP)	Disseminated Intravascular Coagulation (DIC)	Hemolytic Uremic Syndrome (HUS)
Any Grade 4 anemia regardless of underlying mechanism		
Hepatic (reported as ECI if \geq Grade 2, or any grade resulting in dose modification or use of systemic steroids to treat the AE)		
Hepatitis	Autoimmune hepatitis	Transaminase elevations (ALT and/or AST)
Infusion Reactions (reported as ECI for any grade)		
Allergic reaction	Anaphylaxis	Cytokine release syndrome
Serum sickness	Infusion reactions	Infusion-like reactions
Neurologic (reported as ECI for any grade)		
Autoimmune neuropathy	Guillain-Barre syndrome	Demyelinating polyneuropathy
Myasthenic syndrome		
Ocular (report as ECI if \geq Grade 2 or any grade resulting in dose modification or use of systemic steroids to treat the AE)		
Uveitis	Iritis	
Renal (reported as ECI if \geq Grade 2)		
Nephritis	Nephritis autoimmune	Renal Failure
Renal failure acute	Creatinine elevations (report as ECI if \geq Grade 3 or any grade resulting in dose modification or use of systemic steroids to treat the AE)	
Skin (reported as ECI for any grade)		
Dermatitis exfoliative	Erythema multiforme	Stevens-Johnson syndrome
Toxic epidermal necrolysis		
Skin (reported as ECI if \geq Grade 3)		
Pruritus	Rash	Rash generalized
Rash maculopapular		
Any rash considered clinically significant in the physician's judgment		

Other (reported as ECI for any grade)		
Myocarditis	Pancreatitis	Pericarditis
Any other Grade 3 event which is considered immune-related by the physician		

Events of clinical interest for this study include:

- An overdose of pembrolizumab (see **Section 7.3.2**) that is not associated with clinical symptoms or abnormal laboratory results.
- An elevated AST or ALT lab value that is greater than or equal to 3X the upper limit of normal and an elevated total bilirubin lab value that is greater than or equal to 2X the upper limit of normal and, at the same time, an alkaline phosphatase lab value that is less than 2X the upper limit of normal, as determined by way of protocol-specified laboratory testing or unscheduled laboratory testing (see **Section 6.3.7**).

Non-serious Events of Clinical Interest will be forwarded to Merck Global Safety and will be handled in the same manner as SAEs (see **Section 10.2.2**).

10.4 Investigator Reporting: Notifying the Study Sponsor

Investigators **MUST** report within 24 hours upon becoming aware, to the sponsor ANY Serious Adverse Events, whether or not they are considered related to the investigational agent(s)/intervention.

SAE reports and any other relevant safety information are to be forwarded to the Merck Global Safety [contact].

10.4.1 Reporting Events of Clinical Interest (ECIs)

ECIs (both non-serious and serious adverse events) identified in the Event of Clinical Interest Guidance Document from the date of first dose of pembrolizumab through 90 days following cessation of treatment, or 30 days following cessation of treatment if the participant initiates new anticancer therapy, whichever is earlier, need to be reported within 24 hours to the Sponsor and within 2 working days to Merck Global Safety, regardless of attribution to study treatment, consistent with standard SAE reporting guidelines.

Attn: Worldwide Product Safety

[contact]

Reporting of Overdose

All reports of overdose with and without an adverse event must be reported within 24 hours to the Sponsor and within 2 working days hours to Merck Global Safety. (Attn: Worldwide Product Safety; [contact]).

Reporting of Pregnancy and Lactation

Although pregnancy and lactation are not considered adverse events, it is the responsibility of investigators or their designees to report any pregnancy or lactation in a participant (spontaneously reported to them), including the pregnancy of a male participant's female partner

that occurs during the trial or within 120 days of completing the trial, or 30 days following cessation of treatment if the participant initiates new anticancer therapy, whichever is earlier. All participants and female partners of male participants who become pregnant must be followed to the completion/termination of the pregnancy. Pregnancy outcomes of spontaneous abortion, missed abortion, benign hydatidiform mole, blighted ovum, fetal death, intrauterine death, miscarriage and stillbirth must be reported as serious events (Important Medical Events). If the pregnancy continues to term, the outcome (health of infant) must also be reported.

Such events must be reported within 24 hours to the Sponsor and within 2 working days to Merck Global Safety. (Attn: Worldwide Product Safety; [contact]).

10.5 Follow-Up for Serious Adverse Events

All related SAEs should be followed to their resolution, until the study participant is lost to follow-up, the start of a new treatment, or until the study investigator assesses the event(s) as stable or irreversible. New information will be reported when it is received.

10.6 Follow-Up for Events of Clinical Interest

All related ECIs should be followed to resolution. The Adverse Experience eCRF should be updated with information regarding duration and clinical course of the event. Information obtained from the consulting specialist, including diagnosis, should be recorded in the appropriate AE fields. Free-text fields should be used to record narrative information:

- Clinical course of the event
- Course of treatment
- Evidence supporting recovery
- Follow-up to the clinical course

Any treatments administered for the event should also be entered in the Concomitant Medication eCRF.

10.7 Unanticipated Problems

10.7.1 Definition

An Unanticipated Problem (UP) is any incident, experience, or outcome that meets all of the following criteria:

- Unexpected (in terms of nature, severity, or frequency) given:
 - a) The research procedures that are described in the study-related documents, including study deviations, as well as issues related to compromise of participant privacy or confidentiality of data.
 - b) The characteristics of the participant population being studied.

- Related or possibly related to participation in the research (possibly related means there is a reasonable possibility that the incident, experience, or outcome may have been caused by the procedures involved in the research).
- Suggests that the research places participants or others at a greater risk of harm (including physical, psychological, economic, or social harm) than was previously known or recognized and if in relation to an AE is also deemed **Serious** per **Section 10.2**.

10.7.2 Reporting Unanticipated Problems

Unanticipated problem reporting will begin at the time of participant consent. The Unanticipated Problem Form will be submitted to the CRS Compliance Office within 1 business day of becoming aware of the Unanticipated Problem. After review, CRS Compliance will submit the UP to the IRB.

When becoming aware of new information about an Unanticipated Problem, submit the updated information to CRS Compliance with an updated Unanticipated Problem Form. The site Investigator or designated research personnel will report all unanticipated problems, whether related or unrelated to the investigational agent(s) to the **IRB in accordance with their local institutional guidelines**.

10.8 FDA Reporting

When RPCI is the IND holder the following describes the FDA reporting requirements by timeline for AEs and new safety findings that meet the criteria outlined below:

Within 7 Calendar Days

Any adverse event that meets **ALL** the following criteria:

- Related or possibly related to the use of the study drug;
- Unexpected; and
- Fatal or life-threatening.

Within 15 Calendar Days

Any adverse event that meets **ALL** the following criteria:

- Related or possibly related to the use of the study drug;
- Unexpected; and
- Serious but not fatal or life-threatening;

Or, meets **ANY** of the following criteria:

- A previous adverse event that is not initially deemed reportable but is later found to fit the criteria for reporting (report within 15 days from when event was deemed reportable).
- Any findings from other studies, including epidemiological studies, pooled analysis of multiple studies, or other clinical studies conducted with the study drug that suggest a significant risk in humans exposed to the drug.

- Any findings from animal or in vitro testing that suggest a significant risk for human participants including reports of mutagenicity, teratogenicity, or carcinogenicity or reports of significant organ toxicity at or near the expected human exposure.
- Any clinically important increase in the rate of occurrence of a serious, related or possibly related adverse event over that listed in the protocol or investigator brochure.

Sponsors are also required to identify in IND safety reports, all previous reports concerning similar adverse events and to analyze the significance of the current event in the light of the previous reports.

Reporting Process

The principal investigator or designee will complete and submit a FDA Form 3500A MedWatch for any event that meets the above criteria. Forms will be submitted to the CRS Compliance Office via email to [contact].

11 DATA AND SAFETY MONITORING

The RPCI Data and Safety Monitoring Board will assess the progress of the study, the safety data, and critical efficacy endpoints. During the Phase Ib study, the study conduct will be reviewed by the RPCI Phase I Committee on a weekly basis. The DSMB will review the study annually and will make recommendations that include but not limited to; (a) continuation of the study, (b) modifications to the design (c) or termination of the study.

12 STATISTICAL METHODOLOGY

This is a single-arm phase Ib\II study of pembrolizumab and cetuximab in patients with metastatic colorectal cancer.

The primary objectives of this study are:

- To estimate the objective response rate of patients with metastatic colorectal cancer treated with pembrolizumab and cetuximab
- To estimate the 6-month progression-free survival (PFS) rate of patients with metastatic colorectal cancer treated with pembrolizumab and cetuximab
- To examine the adverse event profile of combining pembrolizumab and cetuximab

The secondary (exploratory) objectives of this study are:

- To examine the PFS of patients with metastatic colorectal cancer treated with pembrolizumab and cetuximab
- To examine the overall survival of patients with metastatic colorectal cancer treated with pembrolizumab and cetuximab
- To determine estimate the objective response rate by immune-related response criteria (irRECIST) of patients with metastatic colorectal
- To explore peripheral blood and tumor biomarkers of response and/or resistance to the study treatment

12.1 Sample Size Determination

We utilize two primary efficacy endpoints for this study: the proportion of patients achieving complete or partial RECIST objective response rate and the proportion surviving progression-free for at least six months. While the addition of pembrolizumab to cetuximab may have cytotoxic effect, it may act primarily in a cytostatic fashion; therefore, it is important to consider both endpoints, and thus declare the agent worthy of further investigation if it shows activity on either endpoint. We utilize a single-stage version of the bivariate design of Sill, et al (24) (2012). Based on historical data, the response rate for cetuximab alone in this patient population is approximately 20%, and the proportion of patients surviving progression-free for at least six months is approximately 30% (5). We set the following null and alternative hypotheses indicating inactivity or activity for the two endpoints.

Endpoint	H₀ (regimen inactive)	H₁ (regimen active)
Objective tumor response	20%	40%
6-Month PFS	30%	50%

We will target 42 eligible and treated patients, but will require at least 38 eligible and treated patients in order to have $\geq 80\%$ power to detect activity based on response alone, $\geq 80\%$ power to detect activity based on 6-month PFS alone, and $\geq 97\%$ power if the regimen is active on both endpoints. This assumes independence of the two endpoints; slight losses of power occur for moderate dependence between the two endpoints. Type I error is controlled at < 0.10 . An exact binomial test will be used to compare the observed response and 6-month PFS percentages versus the null values in the table above. Only patients who are not treated with study therapy will be replaced.

12.2 Demographics and Baseline Characteristics

Descriptive statistics (as appropriate: n, percent, mean, median, min and max) will be used to summarize demographic and baseline characteristics.

12.3 Efficacy Analysis

Objective tumor response and six-month PFS will be tabulated and will be compared to the null values using exact tests. All treated patients with study therapy will be considered evaluable for response and 6-month PFS. Patients who receive at least one full dose of both drugs and come off study therapy prior to 6 months and receive off-protocol therapy will be considered treatment failures with regard to the 6-month PFS endpoint. Patients who have infusions reactions to cetuximab, such that continuation of treatment is not deemed feasible, will be replaced.

All patients treated with study therapy will be considered evaluable for response and 6-month PFS. Patients who come off study therapy prior to 6 months and receive off-protocol therapy will be considered treatment failures with regard to the 6-month PFS endpoint. Objective tumor response will not be considered after patient receives off-study therapy.

Objective tumor response using immune-related RECIST (irRECIST) will be tabulated.

Analysis of secondary endpoints will be hypothesis generating and descriptive in nature. Distributions of PFS and OS will be estimated using the Kaplan-Meier method.

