4.2 Target Accrual and Study Duration

A maximum of 42 participants at 3 sites, including RPCI will be enrolled. Accrual is expected to take up to 4 years, with an expected minimum six months of follow-up for all patients; for study duration of approximately 4 years.

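### One sentence in 12.3 replaces treated cetuximab infusion reactors, against 12.1 and the rest of 12.3, and leaves open whether they stay in the primary denominator

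*Combined protocol and SAP*

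**What the plan says.** Section 12.1 sizes the trial on treated patients, "We will target 42 eligible and treated patients, but will require at least 38 eligible and treated patients", and closes with the replacement rule "Only patients who are not treated with study therapy will be replaced".

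Section 12.3 has two overlapping paragraphs.

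- The first opens with "All treated patients with study therapy will be considered evaluable for response and 6-month PFS". Its 6-month PFS failure rule covers "Patients who receive at least one full dose of both drugs and come off study therapy prior to 6 months" who then receive off-protocol therapy. It ends with "Patients who have infusions reactions to cetuximab, such that continuation of treatment is not deemed feasible, will be replaced".
- The second repeats the evaluability rule, "All patients treated with study therapy will be considered evaluable for response and 6-month PFS", and gives the failure rule with no minimum dose: "Patients who come off study therapy prior to 6 months and receive off-protocol therapy will be considered treatment failures".

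Section 4.2 sets the enrolment limit: "A maximum of 42 participants at 3 sites, including RPCI will be enrolled". Section 6.1 has cetuximab given before pembrolizumab on day 1. Section 1.5 puts cetuximab infusion reactions at up to 4.5%. No section gives the share that ends treatment.

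**The concern.** A patient who reacts to a cetuximab infusion has received study therapy. Under 12.1 that patient is not replaced; under the last sentence of the first paragraph of 12.3 the patient is. The plan is silent on the question that matters for the test: does a replaced reactor stay in the denominator, and with what outcome?

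If the reactor is taken out, membership of the primary analysis set depends on whether continuation was judged feasible. That judgement is made after treatment starts, by people who know the treatment, with no criterion stated. Those removed have had little treatment and are likely to be failures, so removal raises the observed rates. In a single-arm trial that goes forward on either of two endpoints, a shift of one patient at the cut-off can change the conclusion.

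The failure rule adds to this. A patient whose first cetuximab infusion is stopped may never receive a full dose of both drugs. The narrower version of the rule does not reach that patient; the unqualified version does.

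**Working it through.** **Inputs (12.1).** Response 20% under the null and 40% under the alternative; 6-month PFS 30% and 50%; GO if either endpoint is positive; exact binomial tests; independence; overall type I error below 0.10; power at least 80% on either endpoint alone and at least 97% on both. The plan gives neither sidedness nor cut-offs. One-sided upper tails are assumed.

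**1. Reproduce the design.** With X responses (cut-off a) and Y patients progression-free at 6 months (cut-off b),

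P(GO) = 1 − [1 − P(X ≥ a)] × [1 − P(Y ≥ b)].

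A search of all pairs finds 38 as the smallest n that meets every stated condition, so the plan's sample sizes reproduce. From 38 to 42 one pair qualifies at each n:

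| n | a / b | Type I error |
|---|---|---|
| 38 | 12 / 17 | 0.0986 |
| 39 | 13 / 17 | 0.0837 |
| 40 | 14 / 17 | 0.0815 |
| 41 | 13 / 18 | 0.0913 |
| 42 | 14 / 18 | 0.0808 |

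Check at n = 42:
- type I error: 1 − (1 − 0.0298)(1 − 0.0526) = 0.081;
- response only: 1 − (1 − 0.8509)(1 − 0.0526) = 0.859;
- PFS only: 1 − (1 − 0.0298)(1 − 0.8600) = 0.864;
- both active: 1 − (1 − 0.8509)(1 − 0.8600) = 0.979.

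**2. Boundary results with 42 treated and no substitutes.** The other endpoint is below its cut-off, and reactors fail the endpoint shown.

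| Reactors | Removed | Kept |
|---|---|---|
| 1 | 13/41 responses, cut-off 13, p = 0.052: GO | 13/42, cut-off 14, p = 0.062: NO-GO |
| 2 | 17/40 at 6-month PFS, cut-off 17, p = 0.063: GO | 17/42, cut-off 18, p = 0.097: NO-GO |

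A different inferred rule, 0.05 one-sided per endpoint, behaves alike: 18/41 at 6-month PFS is GO (p = 0.041) and 18/42 is NO-GO (p = 0.053). That rule narrowly misses the stated power at n = 42 (0.786 for PFS only, 0.967 for both).

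**3. How often the readings disagree.** Let R reactors fail both endpoints and let the other 42 − R have the rates shown. Each difference is P(GO, removed) − P(GO, kept). The reverse disagreement has probability 0 in every row.

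| True rates (response / PFS) | R = 1 | R = 2 |
|---|---|---|
| 20% / 30% | 0.0913 − 0.0645 = 2.7% | 0.0815 − 0.0507 = 3.1% |
| 40% / 30% | 0.8989 − 0.8293 = 7.0% | 0.8022 − 0.7956 = 0.7% |
| 20% / 50% | 0.8346 − 0.8298 = 0.5% | 0.8685 − 0.7894 = 7.9% |
| 40% / 50% | 0.9816 − 0.9689 = 1.3% | 0.9717 − 0.9546 = 1.7% |

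**4. If substitutes are enrolled.** Now compare 42 with reactors removed against 42 + R with reactors kept. With one reactor, 14/18 still qualifies at n = 43, so nothing need change. At n = 44 the qualifying pairs are 14/19, 15/18 and 15/19; each raises at least one cut-off, so a boundary result on that endpoint could flip, but 18/44 at 6-month PFS stays GO under 15/18. At 0.05 per endpoint the cut-offs stay at 14/19 through n = 44.

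**5. Type I error, conditional.** Suppose reactors are removed at rate q and fail both endpoints, and the 20% and 30% nulls are rates among all treated patients. The null rates among those retained become 0.20/(1 − q) and 0.30/(1 − q). At n = 42 with cut-offs 14/18:

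| q (assumed) | Independent | Responders nested in 6-month PFS |
|---|---|---|
| 0 | 0.081 | 0.065 |
| 1% | 0.088 | 0.070 |
| 2% | 0.096 | 0.076 |
| 4.5% | 0.118 | 0.094 |

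At q = 2% under independence: 1 − (1 − 0.0348)(1 − 0.0629) = 0.096.

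**The case against.** Most of 12.1 and 12.3 agrees. Replacing only the untreated and calling all treated patients evaluable are one position; a single sentence departs from it. A reader might infer three competing rules, but the text supports two.

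A reader might also take replaced to mean excluded. The plan does not say so. Since 12.3 calls all treated patients evaluable both before and after that sentence, enrolling a substitute while keeping the reactor in the denominator is a coherent reading, and there is then no inflation by this route. This stands: the fault is an unanswered question, not a stated exclusion.

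The one- and two-reactor flips need removal without substitution, which mixes the replacement sentence with the enrolment cap. They also need cut-offs that the plan does not state, and failure by the reactors. Failure is not automatic: 6.1 allows pembrolizumab on day 2 after a cetuximab infusion reaction, and 6.6 follows patients who stop without progression for disease status. These limits stand.

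The two failure sentences do not contradict each other. The unqualified one contains the other, so applying both gives one answer. The difficulty arises only if the narrower one is taken as the operative rule.

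Finally, treatment-ending reactions may be rare. The 4.5% is an upper figure for infusion reactions, and prior severe reactors are excluded (5.2). That bears on size. It does not say which patients are in the denominator.

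**Conclusion.** The inconsistency is in the current text and should be fixed. Section 12.3 replaces a group of treated patients whom 12.1 does not replace, and the plan does not say whether they count.

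The effect is confined to results at the cut-off. With inferred cut-offs, 42 treated, no substitution, and one or two reactors who fail both endpoints, the readings disagree with probability of about 0.5% to 8% across the stated null and alternative rates, always towards GO under removal. With actual substitution, one or two reactors need not change the decision.

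A reader might infer that the trial's type I error exceeds 0.10. The documents do not support that as a general statement. It needs removal, nulls that are all-treated rates, failure on both endpoints, independence, and a high enough exclusion rate. At n = 42 the error is 0.096 at 2% and 0.118 at 4.5%, and it stays below 0.10 throughout this range if responders are nested within 6-month PFS. The rate of treatment-ending reactions is not given, so these rates are assumptions. The sample size itself is not in question.

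**What to change.** In 12.3, delete the infusion-reaction replacement sentence and the version of the failure rule that requires a full dose of both drugs. Use one rule in 12.1 and 12.3:

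> All eligible patients who receive any study therapy are in the denominator of both primary endpoints, including those who stop for an infusion reaction. A patient without a confirmed CR or PR before off-protocol therapy is a non-responder. A patient who starts off-protocol therapy before 6 months is a 6-month PFS failure. Only patients who receive no study therapy are replaced.

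Report an analysis without the reactors as sensitivity only.

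The cost is wording and slightly lower observed rates: in the two-reactor example, 17/42 = 40.5% instead of 17/40 = 42.5%. Power may also fall. If the 40% and 50% alternatives hold only for patients able to continue, all rates are multiplied by 1 − q. At n = 42 with cut-offs 14/18, power on response alone is 0.833 at q = 2% and 0.796 at 4.5%; on PFS alone it is 0.833 and 0.789. The stated power should be qualified to that extent.
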